7.1.3. Safety Laboratory Assessments

All safety laboratory assessments will be conducted at laboratories local to the study sites. To help monitor for potential event of organ transplant rejection in the SOT recipients, safety laboratory assessments will be performed, including assessments related to kidney and liver function (eg, serum creatinine, urine protein, and UPCR for kidney SOT recipients; and ALT, AST, ALP, and bilirubin for liver SOT recipients) at prespecified study visits. After Day 57 (unvaccinated SOT recipients who receive 2 vaccine doses [Group A1]) or after Day 113 (unvaccinated SOT recipients who receive 3 vaccine doses [Group A2]) or after Day 29 (previously vaccinated SOT recipients who receive dose 3 [Group A3] in Part A or SOT recipients who completed the primary vaccination series who receive BD [Group B4]) in Part B, the investigator will review standard-of-care laboratory assessments related to kidney and liver function (as applicable), and report any laboratory-related AEs and suspected or confirmed events of organ transplant rejection until the EOS. The investigator must review results of safety laboratory assessments as soon as they are available. Schedules of sampling for safety laboratory assessments are presented in the SoEs- ([Section 10.1](#)).

A point-of-care urine pregnancy test will be performed at the screening visit (Day 0) and before each dose of vaccine. One pregnancy test is sufficient if Day 0 and Day 1 are combined in the same. At any time, a pregnancy test either via blood or point-of-care urine can be performed, at the discretion of the investigator. Pregnancy is one of the exclusion criteria ([Section 4.1.1.2](#) and [Section 4.1.2.2](#)) in this study and is a reason for dosing discontinuation ([Section 6.2](#)). Appendix 3 ([Section 10.3](#)) details the study guidance on contraception.

7.1.4. Vital Sign Measurements

Vital sign measurements will include systolic and diastolic blood pressure, heart rate, respiratory rate, and body temperature (preferred route is oral). The participant will be seated for at least 5 minutes before all measurements are taken. Vital signs will be measured at the time points

indicated in the applicable SoE. At dosing visits, vital sign measurements will be collected once before injection and at least 30 minutes after injection (before participants are discharged from the study site).

Febrile participants at dosing visits (fever is defined as a body temperature $\geq 38.0^{\circ}\text{C}/\geq 100.4^{\circ}\text{F}$) may have visits rescheduled within the relevant study visit windows. Afebrile participants with minor illnesses may be injected at the discretion of the investigator.

When procedures overlap and are scheduled to occur at the same time point, the order of procedures should be vital sign measurements and then the blood collection.

7.1.5. Physical Examinations

A full physical examination, including height and weight, will be performed at Day 1 as indicated in the applicable SoE ([Section 10.1](#)). The full examination will include assessment of skin, head, ears, eyes, nose, throat, neck, thyroid, lungs, heart, cardiovascular system, abdomen, lymph nodes, and musculoskeletal system/extremities. Any clinically significant finding identified during a study visit should be reported as an MAAE. Symptom-directed physical examinations will be performed at other time points.

On each injection day before injection and again 7 days after injection, the arm that received the injection should be examined and the associated lymph nodes must be evaluated. Any clinically significant finding identified during a study visit should be reported as an MAAE.

Body mass index will be calculated at the screening visit (Day 0) only.

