2. OBJECTIVES AND ENDPOINTS

The objectives which will be evaluated in this study and endpoints associated with each objective are provided in [Table 1](#).

Table 1: Study Objectives and Endpoints

Objectives	Endpoints
Part A	
Primary Objectives	Primary Endpoints

• To evaluate the safety of 100 µg mRNA-1273 administered in 2-dose or 3-dose regimens	
• Unsolicited adverse events (AEs) through 28 days after each injection• Medically attended adverse events (MAAEs) from Day 1 and throughout the study period• Serious adverse events (SAEs) from Day 1 and throughout the study period• Adverse events of special interest (AESIs) from Day 1 and throughout the study period• AEs leading to discontinuation from dosing and/or study participation (withdrawal) on Day 1 and throughout the study period• Biopsy-proven organ rejection from Day 1 and throughout the study period

• To evaluate the reactogenicity of 100 µg mRNA-1273 administered in 2-dose or 3-dose regimen	
• Solicited local and systemic adverse reactions (ARs) through 7 days after each injection (for unvaccinated participants who received 2 doses of mRNA-1273)• Solicited local and systemic ARs through 7 days after each injection (for unvaccinated SOT recipients who received 3 doses and SOT recipients previously vaccinated outside the study who received a third dose)

• To evaluate serum neutralizing antibody (nAb) responses to doses of 100 µg mRNA-1273 obtained	
• The geometric mean titer (GMT) value of serum Severe Acute Respiratory Syndrome coronavirus 2 (SARS-CoV-2)-specific nAb

Objectives	Endpoints
28 days after the second dose or third dose	
level after the second dose (Day 57 for unvaccinated participants [])
 
 • The GMT value of SARS-CoV-2-specific nAb level 28 days after dose 3 (Day 113 for unvaccinated SOT recipients and Day 29 for previously vaccinated SOT recipients)
Secondary Objectives	Secondary Endpoints

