
 To define, in a subset of SOT recipients who received 3-dose regimen and healthy participants, the epitopes recognized by B-cells and antibodies generated in response to mRNA-1273 	
 Magnitude and phenotype of S protein-specific B-cells as measured by flow cytometry at Day 1, Day 36, and Day 92 for unvaccinated SOT recipients, at Day 1 and Day 8 for previously vaccinated SOT recipients, and at Day 1 and Day 36 in healthy participants Determination of targeted major antigenic sites and amino acid residues on SARS-CoV-2 S protein

Objectives	Endpoints
Part B – Booster Phase	
Primary Objectives	Primary Endpoints

• To evaluate the safety of the 100 µg BD of mRNA-1273	
• Solicited local and systemic ARs through 7 days after BD injection• Unsolicited AEs through 28 days after BD injection• MAAEs throughout the study period• SAEs throughout the study period• AESIs, including myocarditis/pericarditis throughout the study period• AEs leading to discontinuation from dosing and/or study participation (withdrawal) throughout the study period• • Biopsy-proven organ rejection throughout the study period

• To evaluate serum nAb responses elicited by the 100 µg mRNA-1273 obtained 28 days after the BD	
• The GMT value of serum SARS-CoV-2-specific nAb level 28 days after the BD in SOT participants who received the Moderna primary series• The GMT value of SARS-CoV-2-specific nAb level 28 days after BD in SOT participants who received non-Moderna primary series
Exploratory Objectives	Exploratory Endpoints

• To evaluate the persistence of the immune response of the BD of mRNA 1273 vaccine (100 µg) as assessed by the level of SARS-CoV-2 S2P specific bAb through 6 months after BD	
• The GM value of SARS-CoV-2 S2P specific bAb on BD-Day 1, BD-Day 29 (28 days after BD), BD-Day 181 (6 months after BD)

Objectives	Endpoints

 To evaluate the persistence of the immune response of the BD of mRNA 1273 vaccine (100 µg) as assessed by the level of nAb through 6 months after BD 	
 The GM values of SARS-CoV-2-specific nAb on BD-Day 1, BD-Day 29 (28 days after BD), BD-Day 181 (6 months after BD)

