7.5.4. Medically Attended Adverse Events

A MAAE is an AE that leads to an unscheduled visit to an HCP. This would include visits to a study site for unscheduled assessments (eg, abnormal laboratory test results follow-up, COVID-19 [[Section 7.3.1](#)]) and visits to HCPs external to the study site (eg, urgent care, primary care physician). Investigators will review unsolicited AEs for the occurrence of any MAAE. Unsolicited AEs will be captured on the AE page of the eCRF.

All confirmed COVID-19 cases ([Section 7.3.1](#)) will be recorded as MAAEs and reported to the Sponsor or designee immediately and in all circumstances within 24 hours, using the SAE Mailbox, the SAE Hotline, or the SAE Fax line ([Section 7.5.12](#)). The investigator will submit any updated COVID-19 case data to the Sponsor within 24 hours of it being available.

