3. If the visit for the second dose (Day 29) is disrupted and cannot be completed at Day 29 -3/+7 days as a result of the COVID-19 pandemic (self-quarantine or disruption of study site activities following business continuity plans and/or local government mandates for “stay at home” or “shelter in place”), the visit window may be extended to Day 29 + 21 days. When the extended visit window is used, the remaining clinic study visits D36 (last dose + 7 days), D57 (last dose + 28 days), 6 month visit (last dose + 180 days), and 12 month visit (last dose + 365 days) should be rescheduled to follow the scheduled inter-visit interval from the actual date of the second dose. The timing of eDiary follow-ups and safety calls will not be adjusted. Additional safety calls every 4 weeks should be scheduled if there is a gap beyond 28 days between the last safety call and the last study visit. Participants who agree to receive a booster dose in Part B of the study will follow the schedule of events for Part B (see [Table 10](#)).
4. Safety follow-up via an eDiary questionnaire will be performed every 4 weeks from Day 71 to Day 183 and again from Day 223 to Day 363.
5. Safety follow-up via a safety telephone call will be performed every 4 weeks from Day 85 to Day 197 and again from Day 237 to Day 377.
6. Physical examination: A full physical examination, including height and weight, will be performed to determine eligibility prior to administration of vaccine dose on Day 1. Body mass index will be calculated only at the screening visit (Day 0). Symptom-directed physical examinations will be performed at Day 29, Day 57, Day 209, and Day 394. Any clinically significant finding identified during a study visit should be reported as an MAAE.
7. On each injection day before injection and again 7 days after injection, the arm that received the injection should be examined and the associated lymph nodes must be evaluated. Any clinically significant finding identified during a study visit should be reported as an MAAE.

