Recording of suspected AND confirmed organ transplant rejection ¹⁷	X	X	X	X	X	X	X
Recording of concomitant medications and nonstudy vaccinations ¹⁷	X	X	X	X	X	X	X
Recording of concomitant immunosuppressant medications ¹⁸	X	X	X	X	X	X	X

Abbreviations: AE = adverse event; AESI = adverse event of special interest; AR = adverse reaction; BD = booster dose; C = clinic visit; D = day; eDiary = electronic diary; ICF = informed consent form; MAAE = medically attended AE; NP = nasopharyngeal; SAE = serious adverse event; SC = safety (phone) call; SOTr = solid organ transplant recipients.

Note: In accordance with FDA Guidance on Conduct of Clinical Trials of Medical Products during COVID-19 Public Health Emergency (DHHS 2020), investigators may convert study site visits to home visits or telemedicine visits with the approval of the Sponsor.

1. A BD may be administered to all eligible participants who are currently enrolled in Part A or Part B provided there are no current contraindications for further dosing ([Section Error! Reference source not found.](#)). A participant who is currently in the Convalescent Period may come in for a BD-1 visit and receive a BD as long they are no longer symptomatic, and this includes the possibility for a Convalescent Visit Day 28 to overlap and be combined with a BD-1 visit. For eligible participants in Part A who are at least 4 months from completion of primary vaccination series who consent to receive BD, the study visit or follow-up 4 months after their last dose in Part A may overlap with BD-D1. In this case, a participant will need to come in for the BD-D1 visit at least 4 months after the last dose and then follow Part B.

2. Symptom-directed physical examination will be performed at the BD-Day 1. At visits BD-2 (BD-D29), and BD-3 (BD-D181), a symptom-directed physical examination may be performed at the discretion of the investigator. Any clinically significant finding identified during a study visit should be reported as a MAAE.
3. On dosing day before injection, the arm receiving the injection should be examined and the associated lymph nodes should be evaluated.

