### **6.3.1. Adverse Events**

Unsolicited AEs are collected for the purpose of assessing safety. All safety analyses will be based on the Safety Set.

A treatment-emergent AE (TEAE) is defined as any event occurring during the study not before exposure to study vaccine or any event already present that worsens after exposure to study vaccine. Worsening of a pre-existing condition after vaccination will be reported as a new AE.

Adverse events will also be evaluated by the investigator for the coexistence of MAAE which is defined as an AE that leads to an unscheduled visit to a healthcare practitioner.

Unsolicited AEs will be coded by PT and SOC using MedDRA and summarized by participant group and analysis stage (up to 28 days after any vaccination and throughout the study period from Day 1 (Part A)/BD-Day 1 (Part B)/Day 1 (Part A and Part B); see [Section 6.1](#) for definitions of participant group and analysis stage).

Similarly, adverse events related to organ rejection status will be reviewed by an adjudication committee as described in Section 7.6.1 of Protocol Amendment 4 to determine whether they represent an adjudicated biopsy-proven organ rejection. Events that are adjudicated as biopsy-proven organ rejection will be summarized for transplant recipients by participant group and analysis stage. Adjudication results will be listed.

All summary tables (except for the overall summary of AEs) for unsolicited AEs will be presented by SOC and PT for TEAEs with counts of subjects included. SOC will be displayed in internationally agreed order. PT will be displayed in descending order of frequency, overall, and then alphabetically within SOC. When summarizing the number and percentage of subjects with an event, subjects with multiple occurrences of the same AE or a continuing AE will be counted once. Subjects will be presented according to the highest severity (the strongest relationship) in the summaries by severity/grade (of related AEs), if subjects reported multiple events under the same SOC and/or PT.

Percentages will be based upon the number of subjects in the Safety Set within each participant group.

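### MAAE reporting instruction and MAAE definition disagree, so a primary safety percentage would mix two kinds of event; the direction is upward, the size is unknown and probably small

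*Protocol*

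**What the plan says.** **Endpoint status.** Protocol Section 2 lists "Medically attended adverse events (MAAEs) from Day 1 and throughout the study period" among the Part A primary safety endpoints and "MAAEs throughout the study period" among those for Part B. SAP 3.1 carries both over.

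**Definition.** Protocol 7.5.4: "A MAAE is an AE that leads to an unscheduled visit to an HCP". On study-site visits it adds: "This would include visits to a study site for unscheduled assessments". SAP 6.3.1 has the investigator evaluate adverse events for an "MAAE which is defined as an AE that leads to an unscheduled visit to a healthcare practitioner".

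**Reporting instruction.** Protocol 7.1.5 says, once after the full examination and again after the arm and lymph-node check: "Any clinically significant finding identified during a study visit should be reported as an MAAE". The sentence recurs in Table 7 (footnotes 6 and 7), Table 8 (6 and 7) and Table 9 (5 and 6). Table 10 footnote 2 has: "Any clinically significant finding identified during a study visit should be reported as a MAAE". These footnotes sit beside scheduled examinations; Table 7 footnote 6, for example, states "Symptom-directed physical examinations will be performed at Day 29, Day 57, Day 209, and Day 394".

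**Analysis.** SAP 6.3.1.1 and 6.3.1.2 tabulate unsolicited medically attended treatment-emergent events as number and percentage of participants, by participant group. SAP Section 7 records no change from the protocol's planned analyses.

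**The concern.** An MAAE as defined tells the reader that something sent a participant to seek care outside the schedule. A finding picked up because the protocol put an examiner in front of the participant tells the reader something else. If both are entered under the same label, the MAAE percentage no longer matches its stated definition, and the excess depends partly on how many examinations a regimen schedules. In a study designed for estimation the reported percentage is itself the result, so its definition needs to be single.

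**Working it through.** The documents state no MAAE rate, so there is no figure to reproduce. The check is mainly a comparison of texts.

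**Step 1: does the instruction reach scheduled visits?** It refers to a study visit without saying scheduled or unscheduled. Its place in 7.1.5 and in the footnotes, next to fixed examination days, means that scheduled visits are included.

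**Step 2: where do the two rules differ?**

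| Clinically significant examination finding | 7.1.5 and footnotes | 7.5.4 and SAP 6.3.1 |
|---|---|---|
| Leads to an unscheduled HCP visit | MAAE | MAAE |
| Found at a scheduled visit, no unscheduled HCP visit | MAAE | Not an MAAE |

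Only the second row differs, and it can only add to the count.

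**Step 3: does the SAP settle it?** SAP Section 1 says the SAP prevails where methods differ. But the MAAE status it tabulates is the investigator's evaluation, which 7.1.5 steers, and no derivation removes or separates examination-only entries.

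**Step 4: how many scheduled examinations are there?** Counted after the first dose of each part, from Tables 7 to 10 and 7.1.5:

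| Group | Physical examinations | Arm and lymph-node check 7 days after a dose | Total |
|---|---|---|---|
| A2 | D29, 57, 85, 113, 265, 450 (6) | D8, 36, 92 (3) | 9 |
| A1/A5 | D29, 57, 209, 394 (4) | D8, 36 (2) | 6 |
| A3 | D29, 180, 365 (3) | D8 (1) | 4 |
| Part B | BD-D29, BD-D181 (2) | BD-D8 (1) | 3 |

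**Step 5: can the size be derived?** No. It needs the chance q that an examination visit yields a significant finding without unscheduled care, and the documents do not give it. As illustration only, with constant q and independent visits (both assumptions), the share of participants with at least one such event over k visits is 1 − (1 − q)^k. For example, k = 6 and q = 1% gives 1 − 0.99^6 = 5.9%.

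| Group | All visits: q = 0.5% / 1% / 2% | Without the 7-day visits: q = 0.5% / 1% / 2% |
|---|---|---|
| A2 | 4.4 / 8.6 / 16.6% (k = 9) | 3.0 / 5.9 / 11.4% (k = 6) |
| A1/A5 | 3.0 / 5.9 / 11.4% (k = 6) | 2.0 / 3.9 / 7.8% (k = 4) |
| A3 | 2.0 / 3.9 / 7.8% (k = 4) | 1.5 / 3.0 / 5.9% (k = 3) |
| Part B | 1.5 / 3.0 / 5.9% (k = 3) | 1.0 / 2.0 / 4.0% (k = 2) |

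At q = 5% the nine A2 visits give 37.0%. The result is driven by the assumed q, so none of these figures is an estimate for this trial.

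**Step 6: which way do the documents push q?** Down.
- Physical examinations after Day 1 are symptom-directed (7.1.5), not routine screening. Those at BD-D29 and BD-D181 are at the investigator's discretion (Table 10 footnote 2).
- Redness, swelling or axillary tenderness at the 7-day check is a solicited reaction if it began within 7 days. Protocol 7.5.3 puts it on the solicited page even when medically attended, and the SAP MAAE tables are limited to unsolicited events.
- Under 7.5.13 a clinically significant abnormal evaluation should be repeated until normal or stable. Where that needs an unscheduled visit, 7.5.4 is met and the two rules agree.

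**The case against.** The strongest case against acting has four parts.

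- **Broad capture is deliberate.** The protocol assigns other events to MAAE outright: confirmed COVID-19 (7.3.1, 7.5.4), suspected anaphylaxis (7.5.5), and suspected or confirmed rejection (7.5.6). This is fair, but those are named event types. The examination sentence is open-ended, and 7.5.4 does not mention it as an extension.
- **No comparison is planned.** Protocol 8.1 and SAP 4.2 say so, and percentages over the whole study period already differ with length of follow-up under either definition. This stands. The effect is on what the percentage means, not on any inference.
- **Over-reporting is the safe direction.** True for case capture. It does not help someone reading a percentage whose label promises unscheduled care.
- **A simple correction could lose data.** This stands and shapes the fix. Unsolicited AEs are collected only through 28 days after each dose (7.5.8, 7.5.13), and their schedule row ends at D57, D113, D29 or BD-D29. For a non-serious finding at a later visit that is not an AESI, the MAAE sentence may be the only explicit recording route.

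A reader might also infer from the visit counts that the MAAE rate is inflated by some 9% to 17% in A2, or that it rises in step with scheduled visits. The documents do not support that: the per-visit yield is assumed, the 7-day visits contribute little to the unsolicited tables, and the remaining examinations are symptom-directed or discretionary.

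**Conclusion.** The contradiction is real. It appears in the protocol body and in all four schedules, and the SAP leaves it open. MAAE percentages in both parts would mix events that led to unscheduled care with findings that were merely seen at a scheduled visit. The upward direction follows from the text alone, given at least one finding of the second kind. The size cannot be derived and is probably small, a judgement that rests on the symptom-directed and discretionary examinations and on the exclusion of solicited reactions from the MAAE tables. No hypothesis test, sample size or planned comparison is affected. It is a definitional defect in a primary safety endpoint that is cheap to repair, not evidence of a quantified bias.

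**What to change.** **Protocol.** Reconcile 7.1.5 and the examination footnotes of Tables 7 to 10 with 7.5.4. Keep an explicit recording route for clinically significant examination findings through the end of study, including beyond 28 days after a dose. Add an eCRF flag for whether an unscheduled HCP visit occurred. Findings at the pre-dose Day 1 examination should follow 7.5.13, which sends occurrences before dosing to medical history.

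**SAP 6.3.1.** Add that the MAAE tables count events that meet the 7.5.4 definition or that the protocol assigns to MAAE elsewhere (confirmed COVID-19, suspected anaphylaxis, suspected or confirmed rejection). Events reported solely from a scheduled-visit examination are tabulated separately, with the combined count also shown. No event is removed from reporting.

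**Cost.** Wording changes, one eCRF flag (or, for data already entered, one query on MAAEs dated to scheduled visits), and one extra table row.

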7.1.6. Assessments for SARS-CoV-2 Infection

Study participants will have NP samples collected for SARS-CoV-2 testing by RT-PCR at time points specified in the applicable SoE ([Section 10.1](#)). A study illness visit or a consultation will be arranged within 72 hours or as soon as possible to collect an NP or nasal swab sample (NP is preferred) to ascertain the presence of SARS-CoV-2 via RT-PCR if a participant experiences any of the following:

- Signs or symptoms of SARS-CoV-2 infection as defined by the CDC ([CDC 2020a](#))
- Close contact exposure to an individual confirmed to be infected with SARS-CoV-2
- MAAE suggesting a SARS-CoV-2 infection

If the participant had known close contact exposure to COVID-19 (eg, close contact exposure to someone with confirmed COVID-19), it will be captured in the COVID-19 exposure form.

If scheduled, the study illness visit may collect additional clinical information at the investigator's discretion, including but not limited to medical history, physical examination, blood sampling for

clinical laboratory testing, and nasal, saliva, and/or NP swab sampling for viral PCR (including multiplex PCR for respiratory viruses, including SARS-CoV-2) to evaluate the severity of the clinical case. Radiologic imaging studies may be conducted. During this visit, a blood sample will also be collected for immunologic assessment of SARS-CoV-2. All findings will be recorded in the eCRF.

If participants are confirmed to have SARS-CoV-2 infection, the investigator will notify the participant and the participant's primary care physician of the diagnosis. If the study participant does not have a primary care physician, the investigator will assist them in obtaining one. The participant will also be instructed on infection prevention measures consistent with local public health guidance.

Any confirmed symptomatic SARS-CoV-2 infection occurring in participants will be captured as an MAAE along with relevant concomitant medications and details about severity, seriousness, and outcome. Additionally, a convalescent visit will be scheduled approximately 28 days (+7 days) after diagnosis ([Section 7.3.2](#)). At this visit, an NP swab sampling for viral PCR and a blood sample will be collected for potential immunologic assessment of SARS-CoV-2 infection

